5.1.1.2.2 Strategy 2: Without Imputation, Censoring Unresolved SVN

Within each cycle, DSN (days) is defined as the number of days from the date of first ANC value of $<0.5 \times 10^9/L$ observed between start of cycle and end of cycle, to the date of first ANC value $\geq 0.5 \times 10^9/L$ that meets the following criteria: (1) occurs after the ANC value of $<0.5 \times 10^9/L$ and (2) no other ANC values $<0.5 \times 10^9/L$ occur between this day and end of cycle. If no SVN occurs, then the cycle is not used in this analysis. The following censoring rules will be applied in the calculation:

- For a cycle where the SVN event does not resolve by end of the cycle, DSN will be assigned as above except the end date will be the earlier of end of cycle or date of last contact.
- For a cycle where the patient dies, withdraws consent, or is lost to follow-up during the SVN event, DSN will be assigned as above except the end date will be the date of the last ANC assessment prior to the end of study.

For the induction treatment period, the overall DSN (days) is the median value among the DSN (days) from all cycles. The following data handling conventions will apply:

- For those patients where all event duration values are derived from cycles with censored data, the median value for that patient will be the median censored value. It will be considered a censored value;
- For those patients where a subset of event duration values are derived from cycles with censored data, the median value for that patient will be estimated using the Kaplan-Meier method. It will be considered as an observed value (i.e. no censored value);
- For those patients where the median event duration cannot be derived (e.g. ≤ 2 values), the longest event duration amongst all the cycles will be used regardless of censoring, but the corresponding censoring flag will be carried over for analysis.

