5.1.1.2. Duration of Severe (Grade 4) Neutropenia (DSN)

There will be three different strategies for assessing DSN in each cycle. All strategies will be applied to derive the DSN, with strategy 1 considered as the primary, and strategy 2 and strategy 3 being supportive sensitivity analyses. The DSN in Cycle 1 is considered for this primary endpoint. Any unscheduled data and the actual assessment date (rather than visit date) will be included in the derivation of each strategy.

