5.1.1.2.1 Strategy 1: Without Imputation of Missing ANC Values

Within each cycle, the DSN (days) is defined as the number of days from the date of first ANC value of $< 0.5 \times 10^9/L$ observed between start of cycle and end of cycle, to the date of first ANC value $\geq 0.5 \times 10^9/L$ that meets the following criteria: (1) occurs after the ANC value of $< 0.5 \times 10^9/L$ and (2) no other ANC values $< 0.5 \times 10^9/L$ occur between this day and end of cycle. DSN is set to 0 in patients who did not experience SVN in a cycle. Any unscheduled data and the actual assessment date (rather than visit date) will be included in the derivation. The following rules will be applied in the calculation:

- For a cycle where the SVN event does not resolve by end of the cycle, DSN will be assigned as above except the end date will be the end of cycle.
- For a cycle where the patient dies during the SVN event, DSN will be assigned as above except the end date will be the date of death.
- For a cycle where the patient withdraws consent or is lost to follow-up during the SVN event, DSN will be assigned as above except the end date will be the date of the last ANC assessment prior to the end of study.

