6.2.7.1.4 Multiplicity Adjustments

The clinical trial evaluates the objectives defined in terms of the comparison of trilaciclib + E/P/A versus placebo + E/P/A on the primary and key secondary myelosuppression efficacy endpoints in [Sections 5.1.1 and 5.1.2](#).

The multiplicity problem includes the following 5 hypotheses of no effect:

- Hypothesis H_1 . Comparison of trilaciclib + E/P/A versus placebo + E/P/A for duration of severe (Grade 4) neutropenia in Cycle 1.
- Hypothesis H_2 . Comparison of trilaciclib + E/P/A versus placebo + E/P/A for occurrence of severe (Grade 4) neutropenia.
- Hypothesis H_3 . Comparison of trilaciclib + E/P/A versus placebo + E/P/A for all-cause dose reductions in the MAHE composite.
- Hypothesis H_4 . Comparison of trilaciclib + E/P/A versus placebo + E/P/A for occurrence of RBC transfusions on/after Week 5 on study.
- Hypothesis H_5 . Comparison of trilaciclib + E/P/A versus placebo + E/P/A for occurrence of G-CSF administration.

These 5 hypotheses can be grouped into 3 families:

- Family 1 (F_1) includes the hypothesis H_1 .
- Family 2 (F_2) includes the hypothesis H_2 .
- Family 3 (F_3) includes the hypotheses H_3 , H_4 , and H_5 .

[figure not shown]
The 1-sided p-values for these 5 comparisons will be used for the multiple testing procedure.

A Hochberg-based gatekeeping procedure will be utilized to control the global familywise error rate across the 5 null hypotheses in the strong sense at a 1-sided $\alpha=0.025$ level, and it satisfies the positive dependence condition at the 1-sided setting. The procedure is built using the mixture methodology developed in Dmitrienko and Tamhane (2011) and accounts for the logical restrictions among the 5 hypotheses displayed in

Figure 2 by performing multiplicity adjustments in three steps. The logical restrictions can be achieved by defining the parallel set and serial set for each individual hypothesis based the tree-structured procedure introduced by Dmitrienko et al (2007).

- Step 1. The trilaciclib vs placebo comparisons for Family 1 (hypothesis H_1) are performed using a truncated version of the Hochberg procedure. The truncation parameter γ is set to 0.
- Step 2. The trilaciclib vs placebo comparisons for Family 2 (hypothesis H_2) are performed using a truncated version of the Hochberg procedure if H_1 is significant in Step 1. The truncation parameter γ is set to 0.

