In addition to the summary from Kaplan-Meier method, the two-sided p-value will be obtained from the stratified Kaplan-Meier method to account for the stratification factors. The hazard ratio (HR) between the two treatments (trilaciclib vs placebo), together with its 95% CIs will be calculated from a Cox proportional hazard model in which treatment and the stratification factors will be included as fixed effects.

For the time (days) to first occurrence of a MAHE event, a graphical display of cumulative incidence will be presented.

The primary and key secondary efficacy endpoints are based on the ITT analysis set, and the analysis will be repeated for the mITT analysis set and PP analysis set.

For RBC transfusions, subsets of subjects with baseline HGB <9 g/L and ≥ 9 g/L will be provided, as well as a summary of the number of units transfused.

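### The Strategy 2 sensitivity analysis of DSN tests the arms only among patients who had severe neutropenia, so its p-value and hazard ratio are not a randomised check on H1

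*SAP*

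**What the plan says.** H1, the only hypothesis in the first family of the testing sequence, is "Comparison of trilaciclib + E/P/A versus placebo + E/P/A for duration of severe (Grade 4) neutropenia in Cycle 1" (SAP 6.2.7.1.4). SAP 5.1.1.2 defines three ways to derive DSN, "with strategy 1 considered as the primary, and strategy 2 and strategy 3 being supportive sensitivity analyses".

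The strategies treat a patient without SVN differently:

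- Strategy 1 (5.1.1.2.1): "DSN is set to 0 in patients who did not experience SVN in a cycle". Strategy 3 (5.1.1.2.3) has the same rule.
- Strategy 2 (5.1.1.2.2): "If no SVN occurs, then the cycle is not used in this analysis". It also defines a patient-level value across cycles: "For the induction treatment period, the overall DSN (days) is the median value among the DSN (days) from all cycles".

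For Strategy 2, SAP 6.2.7.1.5, the section on robustness of the primary and key secondary analyses, specifies Kaplan-Meier summaries and two comparative outputs. The first is a test: "the two-sided p-value will be obtained from the stratified Kaplan-Meier method to account for the stratification factors". The second is an effect estimate: "The hazard ratio (HR) between the two treatments (trilaciclib vs placebo), together with its 95% CIs will be calculated from a Cox proportional hazard model". Neither section describes the comparison as conditional on SVN or as descriptive only.

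**The concern.** A sensitivity analysis should vary one assumption and keep the question fixed. The assumption that Strategy 2 appears meant to vary is the handling of unresolved episodes, by censoring them. It also changes the question. Strategy 1 asks how many days of severe neutropenia a randomised patient has, counting none as zero. Strategy 2 asks how long an episode lasts in patients who had one.

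Having an episode is a post-randomisation outcome, and its occurrence is the other primary endpoint (H2). If trilaciclib prevents SVN in some patients, the trilaciclib patients left in Strategy 2 are not comparable with the placebo patients left. The prevented episodes, which are the main expected benefit, drop out. The resulting p-value and hazard ratio can neither support nor challenge the Strategy 1 result, yet they would be reported under a robustness heading and could be read as doing so.

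**Working it through.** **Inputs.** From SAP 2.3 (also Protocol 13.1): DSN difference 2 days, SD 2.5, one-sided alpha 0.0125, 90% power, 41 evaluable per arm; SVN 45% on placebo and 11% on trilaciclib; 95% evaluability; final N 106 at 1:1, so 53 per arm. From Protocol 4.3.1: Grade 4 ANC in 43.2% (placebo) and 5.3% (trilaciclib) in the earlier study of the same chemotherapy.

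**The plan's own figure.** For a two-sample t-test with 41 per arm the noncentrality is (2/2.5) × √(41/2) = 3.62. Exact power is 0.907, and with 40 per arm it is 0.899. So 41 per arm (82) is reproduced. For the final N, 100/0.95 = 105.3, rounded up to 106.

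**Patients left in Strategy 2 (expected number = 53 × SVN rate).**

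- Placebo: 53 × 0.45 = 23.9. Trilaciclib: 53 × 0.11 = 5.8. That is about 30 of 106 patients, or 28%.
- Binomial 95% ranges: 17 to 31 and 2 to 11.
- With the earlier study's rates: 22.9 and 2.8.
- With zeros kept, as in Strategies 1 and 3, the comparison is 53 vs 53, with about 29 placebo and 47 trilaciclib patients at zero days.

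The 45% and 11% are rates for any induction cycle, so 24 and 6 match the all-cycle patient-level value. For Cycle 1 alone they are upper bounds. If 50% to 75% of SVN patients have it in Cycle 1 (an assumption), about 12 to 18 and 3 to 4 remain.

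**Precision.** The Cox event is resolution of SVN. With 30 resolved episodes split 24:6, SE(log HR) = 1/√(30 × 0.8 × 0.2) = 0.456. The 95% CI spans a factor of exp(1.96 × 0.456) = 2.4 each way. Power for HR 2 is Φ(0.693/0.456 − 1.96) = 33%. For 80% power the HR must be about exp(2.80 × 0.456) = 3.6.

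**Simulation (illustrative).** There are 53 patients per arm and placebo SVN is 45%. Episode length is assumed to be 1 + Gamma(2, 2.5) days, rounded up. Strategy 2 is represented by a log-rank test among SVN patients (|z| > 1.96, by direction), taking that as the meaning of the stratified Kaplan-Meier p-value.

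| Assumed action of trilaciclib | Strategy 2 significant benefit | Strategy 2 significant harm |
|---|---|---|
| Prevents SVN (to 11%), episode length unchanged | about 4% | not above chance |
| Prevents all shorter episodes, only those over 8 days remain (about 10% SVN) | – | about 60% |
| Prevention gradually less likely as episodes lengthen (about 11%) | – | about 14% |
| Prevents SVN (to 11%) and shortens remaining episodes by 40% | about 42% | about 0% |

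In the first case a one-sided rank test at 0.025 on all patients, zeros kept, has about 98% power. In the second, its power was 85% to 93% across runs.

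The model has one episode per patient, no censoring, no strata and day-level durations. It uses a Mann-Whitney test in place of the planned nonparametric ANCOVA. Scheduled counts fall on Days 1, 3, 8, 15 and the next Day 1 (Protocol Table 9-1). With readings on Days 3, 8, 15 and 22 and onset assumed uniform over Days 6 to 15, the second case falls to about 40% harm.

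**The case against.** The strongest reply is that nothing is decided on Strategy 2. SAP 6.2.7.1.1 tests H1 on Strategy 1. SAP 6.2.7.1.5 repeats that analysis on Strategy 3, which keeps the zeros, and on the mITT and PP sets. Prevention of SVN is tested separately as H2. All of this stands. A reader might infer from the link to H1 that the first test in the sequence, or the error rate, is compromised. The documents do not support that.

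A reader might also infer that Strategy 2 is likely to show harm from an effective drug. That needs trilaciclib to remove the short episodes almost completely and leave the long ones, and the documents give no evidence for this mechanism. That case also gives a mean DSN difference of about 1.7 days, short of the planned 2. Under graded prevention significant harm is about 14%. If remaining episodes also shorten, it is about 0% and Strategy 2 often shows benefit. What stands is that the direction depends on unknown features of the residual episodes.

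Finally, episode length among affected patients is clinically informative. Agreed, which is a reason to describe it and not to test it between arms.

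**Conclusion.** The point holds, as a limited defect in one supportive analysis. The Strategy 2 p-value and hazard ratio compare groups selected on a post-randomisation outcome, in about 28% of the randomised patients, and ignore prevention of SVN. The count of about 24 vs 6 rests on the plan's any-cycle rates and 53 per arm. It is an expected number, not one printed in the documents, and an upper bound if the analysis is run on Cycle 1.

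The contrast of about 4% with about 98% rests on unchanged episode length and the assumed duration distribution. The 0% to about 60% range for significant harm shows only how far the result depends on assumptions; it is not a forecast. The H1 decision, the testing sequence and type I error are not affected.

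**What to change.** In SAP 6.2.7.1.5, delete the between-arm p-value and hazard ratio for Strategy 2. Keep the Kaplan-Meier summaries of episode length by arm, state that they are descriptive and conditional on having SVN, and say whether they refer to Cycle 1 or to the all-cycle patient-level value. Add the same label in 5.1.1.2.2, and in 5.1.1.2 stop calling Strategy 2 a sensitivity analysis of the primary endpoint.

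For the robustness of H1, rely on Strategies 1 and 3, which score no SVN as zero. A further nonparametric ANCOVA is optional. Strategy 1 already runs unresolved episodes to the end of the cycle, so a new version would differ only for patients who die, withdraw or are lost during a Cycle 1 episode, for example by extending those episodes to the end of the cycle.

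One cross-reference needs care: SAP 6.2.7.2.1 borrows the Strategy 2 method for time to first MAHE, so that method should be written out there. The cost is a few lines of SAP text before unblinding, with no new data.

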5.1.1.2.3 Strategy 3: With Imputation of Missing ANC Values

DSN (days) in a cycle is defined as the number of consecutive days with SVN, for patients who experienced several episodes of SVN, the number of days for each episode will be summed up. DSN is set to 0 in patients who did not experience SVN in a cycle.

[figure not shown]
To impute the missing daily ANC value, the following algorithms will be applied in the calculation,

(1) Rules of imputation of missing values at Day 2 of a cycle:

- The ANC before and after the missing day was $\geq 0.5 \times 10^9/L$: the day is ignored as a potential day of severe neutropenia.
- If at either neighboring days the ANCs were $< 0.5 \times 10^9/L$, and both are non-missing, then the missing day is set to severe neutropenia.
- If any of the neighboring days were also missing, severe neutropenia cannot be determined, and the data remains missing.

- (2) Missing ANC values for Days 3-8 in each cycle will be imputed using linear interpolation, any recorded Days measurement will not be replaced. The missing values for Day 3 and Day 8 may be potentially imputed with this algorithm.

Figure 1 Graphical Demonstration of Linear Interpolation

Note: The slopes are calculated for each treatment group, where \bar{Y}_1 and \bar{Y}_2 are the mean of ANC values at relevant timepoint. For a time interval, e.g. interval of Day 1 and Day 8 (inclusive), \bar{Y}_1 is the average of the earliest point in the interval and t_1 is the average of the earliest day in the interval. Similarly, \bar{Y}_2 is the average of the latest point in the interval and t_2 is the average of the latest day in the interval.

- If there are at least two assessments within the interval of Day 3 and Day 8 (inclusive), calculate the slope between the first available ANC value and last available ANC value:
 - If the sign of slope agrees with the sign of slopes calculated from its treatment group, the interpolation will be conducted to appropriate schemes as demonstrated in Fig.1 (a) and Fig. 1(b);
 - If the sign of slope does not agree with the sign of slopes calculated from its treatment group, the interpolation will be done within the patient by using the calculated slope from the observed values.
- If there is only one assessment within the interval of Day 3 and Day 8 (inclusive),
 - If the ANC value is $< 0.5 \times 10^9/L$, then the subsequent missing days will be set to this value;
 - If ANC value is $\geq 0.5 \times 10^9/L$, SVN cannot be determined, and the data remains missing.
- If there is no assessment within the interval of Day 3 and Day 8 (inclusive), SVN cannot be determined, and the data remains missing.

- (3) A similar algorithm as in (1) will be performed to impute missing ANC values for Days 9-15 in each cycle using linear interpolation. Day 8 will be used as the earliest date in the

calculations only if it is recorded; it will be interpolated in this interval. Any other recorded measurements will not be replaced.

- (4) A similar algorithm as in (1) will be performed to impute missing ANC values between Days 16 and end of cycle in each cycle using linear interpolation. Day 15 will be used as the earliest date in the calculations only if it is recorded; it will be interpolated in this interval. Any other recorded measurements will not be replaced.
- (5) For a cycle where the SVN event does not resolve by end of the cycle, all values between the last assessment and the end of cycle are set to SVN.
- (6) For a cycle where the patient dies, during the SVN event, the end date of the SVN is the date of death.

5.1.2. Key Secondary Endpoints

5.1.2.1. Occurrence of RBC Transfusions

Each RBC transfusion with a unique start date on/after 5 weeks on study during the induction treatment period will be defined as a separate event and included in the efficacy analyses. A sensitivity analysis including all events occurring during the entire induction treatment period will also be performed.

Occurrence of an RBC transfusion during the induction treatment period is defined as a binary variable (Yes or No); Yes if total number of RBC transfusion ≥ 1 is observed, No for other scenarios.

5.1.2.2. Occurrence of GCSF Administrations

Administration of GCSF is collected throughout the induction treatment period. Those cycles where GCSF is administered concurrently will be identified by comparing the start and stop dates of each administration of GCSF to the start of cycle and end of cycle. If any of the dates of administration of GCSF overlap with any dates between the start of cycle and end of cycle, that cycle will be considered as having GCSF administered. Data handling conventions for missing start and stop dates are described in [Section 6.2.5](#).

For the induction treatment period, the total number GCSF administrations is the number of induction cycles in which there is at least one GCSF dose administered. If a patient did not have any GCSF use, the value of 0 will be assigned to that patient. The number of induction cycles where GCSF was NOT given is calculated as total number of induction cycles received – total number of induction cycles where GCSF was administered.

Therefore, any occurrence of a GCSF administration during an induction cycle or the induction treatment period is defined as a binary variable (Yes or No); Yes if total number of induction cycles with GCSF administration ≥ 1 is observed, No for other scenarios.

5.1.2.3. All-Cause Dose Reductions

Dose reductions are not permitted for trilaciclib or atezolizumab. Dose reductions for E/P are derived from changes in the protocol-specified dose on the dosing page and correspond to the reductions for toxicity specified in the protocol.

No more than 2 dose reductions of E/P in total are allowed for any patient. Simultaneous reduction in the doses of etoposide and carboplatin will count as 1 dose reduction. For more details see [Section 5.2.1.4](#).

5.1.2.4. Overall Survival

Although OS is a key secondary endpoint, OS will be analyzed with a descriptive intention and will not be factored into multiplicity adjustment as described in [Section 6.2.7.1.4](#). That is, no formal statistical testing will be planned. The analysis of OS will be primarily aimed at showing lack of harm from trilaciclib.

Overall survival is calculated as the time (months) from date of randomization to the date of death due to any cause. Patients who do not die during the study will be censored at the date last known to be alive. Patients lacking data beyond the date of randomization will have their survival time censored at date of randomization. OS will not be censored if a patient receives other anti-tumor treatments after the study drugs.

5.1.3. Supportive Secondary Endpoints

5.1.3.1. Total Number of Major Adverse Hematologic Events (MAHE)

As a composite measure of trilaciclib effect, MAHE is based on a combination of individual components specified in [Table 4](#), which also include details about the derivation or data source for each component. For each component of composite MAHE, its number of events is derived as the number of episodes with a unique start date during the induction treatment period between the date of randomization and the end of the last induction cycle (i.e. last cycle of placebo or trilaciclib plus E/P/A). A patient with absence of an episode will be assigned a value of 0 to the number of events for this component. Then, the total number of MAHE during the induction treatment period is obtained as the summation over all components of composite MAHE during the induction treatment period.

Table 4 Component of MAHE and the Suggested Data Source/Derivation Algorithm

Seq #	Component of MAHE	Details
1	All-cause hospitalizations	Each hospitalization is captured in the AE data of the electronic database. Each recorded Preferred Term (PT) with a unique start date will be counted as an event, e.g. if a patient is hospitalized and several preferred terms are attributed to that hospitalization with the same start date, then the event is only counted once. The event terms are coded using the Medical Dictionary for Regulatory Activities (MedDRA) Version 20.1.
2	All-cause dose reductions	Detailed in Section 5.1.2.3
3	Febrile neutropenia	Detailed in Section 5.1.3.10
4	Prolonged severe (Grade 4) neutropenia (duration > 5 days)	Detailed in Section 5.1.1.2.1 . Each cycle with a duration greater than 5 days will be counted as an event with the date of the first grade 4 lab value defined as the start date for the time-to-first event analysis.

Seq #	Component of MAHE	Details
5	RBC transfusion on/after 5 weeks	Detailed in Section 5.1.2.1

A patient with absence of any episode of MAHE will be assigned a value of 0 for the total number of MAHE. Additionally, a sensitivity analysis will be done for dose reductions and RBC transfusions on/after 5 weeks, that excludes patients who do not start a second cycle of treatment.

Time to first occurrence of a MAHE will be used as a sensitivity analysis in support of the total number of MAHE. It is defined as the first time to observe an event among all the components, starting from the date of randomization. Therefore, for a patient with presence of MAHE, time (months) to first occurrence of a MAHE will be the minimum among the 5 potentially derived durations (i.e. calculated as (date of first occurrence of a MAHE component event – date of randomization + 1)/30). A patient without any MAHE will be censored at the end of the last cycle (i.e. last cycle of placebo or trilaciclib), death, end of study, or date of last contact, whichever is earlier.

